# Inclusion/exclusion criteria

Cohort	Inclusion	Exclusion	Cohort eligibility indicator variable*
ED sepsis cohort (primary analysis cohort)	
 
(1) Age ≥18 years
 
(2) Arrival to an intervention or control ED during study period
 
(3) Met all Sepsis-3 criteria in the ED
 
Acute organ failure in the ED defined by SOFA score while in the ED ,≥2 points above baseline
 
Suspected or confirmed infection while in the ED, based on having both: 
 
i. Administration of ,≥1 IV or IV-equivalent antibiotics while in the ED for suspected infection (i.e. antibiotics not given for prophylaxis)
 
ii. Collection of ,≥1 body fluid cultures while in the ED
 
 
 
	
 
Trauma patient
 
Subsequent eligible ED visit with sepsis after first eligible encounter during an analysis window
 
	cohort_sepsis
All adult ED patients cohort	
 
(1) Age ≥18 years
 
(2) Arrival to an intervention or control ED during study period
 
	
 
Trauma patient
 
Received antibiotics within 6 hours prior to study ED arrival
 
Subsequent eligible ED visit after first eligible encounter during an analysis window
 
Left ED without evaluation or treatment
 
	cohort_all
Sepsis high-risk cohort	
 
Age ≥18 years
 
Arrival to an intervention or control ED during study period
 
First recorded temperature ≥38.0°C
 
First-recorded vital sign data meets ≥2 of:         
 
a. Systolic blood pressure <90 mmHg
 
b. Glasgow Coma Scale (GCS) score <15
 
c. Respiratory rate ≥22 breaths/min or oxygen saturation <85%
 
 
 
	
 
Trauma patient
 
Received antibiotics within 6 hours prior to study ED arrival
 
Subsequent eligible ED visit after first eligible encounter during an analysis window
 
Left ED without evaluation or treatment
 
	cohort_risk

Cohort	Inclusion	Exclusion	Cohort eligibility indicator variable*
Sepsis	(1) Age ≥18 years	(1) Trauma patient	cohort_mimics
mimic	(2) Arrival to an intervention or control ED during study period	(2) Received antibiotics	

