### Primary exposure

The primary exposure is arrival to the ED at the intervention hospital during the post-intervention analysis period rather than the pre-intervention analysis period.

Exposure parameter	Description	Exposure variable
Intervention site	Presentation to ED at intervention or control hospital	intervention_site
Analysis phase	Presentation to ED during pre-intervention analysis period or post-intervention analysis period. Encounters presenting during the wash-in period have a missing variable for this variable.	analysis_phase (value missing if wash-in period)
Study phase	Presentation to ED during pre-intervention analysis period, wash-in period, or post-intervention analysis period. This variable is not used for primary differences-in-differences analyses.	study_phase

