# Secondary outcomes

	Analysis		Outcome
Outcome	cohort	Description	variable
Door-to-antibiotic time	Sepsis	Time (minutes) from ED arrival to administration	abx_lt3h
≤3 hours	cohort	of first IV (or equivalent) antimicrobial while in	
		the ED less than or equal to 180 minutes	
30-day mortality	Sepsis	Key clinical/secondary outcome	mort_30d
	cohort		
1-year mortality	Sepsis		mort_1y
	cohort		
In-hospital mortality	Sepsis		mort_hosp
	cohort		
Hospital charges	Sepsis		hosp_charges
	cohort		
Hosp. length of stay (days)	Sepsis		los_hosp
	cohort		

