#### Primary and secondary outcome analysis covariates

Variables listed below will be included in multivariable adjusted analyses for primary and secondary outcomes listed above. Variables are also included in any associated subgroup and sensitivity analyses for these outcomes. For heterogeneity of treatment effect analyses, where continuous variables are categorized or dichotomized, the corresponding adjustment variable will also be categorized analogously in the adjustment model and for creation of the interaction term.

- Age (age, continuous)
- Female sex (sex, binary)
- Presentation from a long-term care facility (snf, binary)
- Weighted Elixhauser comorbidity score (elixhauser\_vw, continuous)
- Arrival to ED via ambulance (arrival\_mode, binary)
- English is preferred language (english\_preferred\_yn, binary)
- First-available temperature in ED (vs\_temp\_cat, categorical, reference group = 1 [temp 36-38°C])
- First-available systolic blood pressure in ED (**vs\_sbp**, continuous)
- Acute physiology score (aps\_24h, continuous)
- ED SOFA score (**sofa\_ed**, continuous)

• ED-diagnosed infection source (**source\_ed\_final\_simpler**, categorical, reference group = 1 [pneumonia])

**Figure 2.** Adjustment variables for primary & secondary multivariable analyses. The primary exposure is intervention ED arrival post-intervention and the primary outcome is door-to-antibiotic time. White symbols indicate potential confounders or precision variables included in the multivariable model, gray symbols represent an unobserved variable, and blue symbols (other than the outcome) represent an ancestor of outcome not included in the multivariable model.

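### Primary and secondary models, mortality included, adjust for two physiology scores not limited to arrival values, and no planned analysis of those outcomes omits them

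*SAP*

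**What the plan says.** The SAP section on primary and secondary outcome covariates gives one list for all those models. It contains "Acute physiology score (aps\_24h, continuous" and "ED SOFA score (sofa\_ed, continuous", with no time limit on either. Two other items on the list, blood pressure and temperature, are tied to the start of the visit, for example "First-available systolic blood pressure in ED". On other analyses the section says: "Variables are also included in any associated subgroup and sensitivity analyses for these outcomes".

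Exposure begins at the door: "The primary exposure is arrival to the ED at the intervention hospital during the post-intervention analysis period". The cohort table takes SOFA over the ED stay: "Acute organ failure in the ED defined by SOFA score while in the ED". The outcomes that share the list are door-to-antibiotic time, the 3-hour version of it, three mortality outcomes, charges and length of stay. The secondary outcome table labels 30-day mortality "Key clinical/secondary outcome".

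If the parallel-trends pre-test fails, the SAP (Data analysis) weights by a propensity score. That score includes acute physiology score, ED SOFA and an item on whether lactate was checked and raised, among covariates the section calls baseline.

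**The concern.** Code Sepsis changes when blood is drawn, lactate measured, imaging done and antibiotics started (Protocol 5.2). A score built from values recorded after arrival can therefore be a consequence of the intervention.

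- **Primary outcome.** If recorded severity falls because of the protocol, part of that fall appears in the difference-in-differences coefficient as benefit. If it rises, for example because more is measured early, real benefit is lost.
- **Mortality.** Faster antibiotics would be expected to act partly through better early physiology. Adjusting for that physiology blocks part of the effect being estimated.

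Because the list is carried into every sensitivity analysis, nothing planned for these outcomes would show whether the answer depends on the scores.

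**Working it through.** **1. Timing, from the text.** No window for `aps_24h` is defined. The SAP's other 24-hour variables count from ED arrival: `abx_24h` in the safety table is antibiotic receipt in the 24 hours after arrival. Mean door-to-antibiotic time is 170 minutes (SAP, Power), and 24 hours is 1,440 minutes. On the same convention, the window runs far beyond the first antibiotic.

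**2. Are the scores needed for confounding?** In the SAP's graph code, exposure has six parents: arrival mode, Elixhauser score, long-term care, preferred language, age and sex. All six are adjusted, which closes every back-door path in that graph. APS and SOFA are then precision variables, harmless only if exposure does not move them. The graph draws no arrow from exposure to either and gives no reason.

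**3. The yardstick.** The plan has no figure for this bias. It claims 90% power for 16 minutes. A closed-form check with its inputs (SD 75; 1,650 and 2,200 patients per year) gives SE = 75 × √(2/1650 + 2/2200) = 3.45 minutes and a detectable change of (1.96 + 1.28) × 3.45 = 11.2 minutes. The 16 minutes is more conservative than that. The plan's simulation details are not in the documents, so this is not shown to be an error. I use 16 minutes only as a scale.

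**4. Primary bias (all inputs assumed).** Door-to-antibiotic time falls 2–3 minutes per APS point, the protocol shifts recorded APS by 2–3 points either way, score reliability is 0.6–1.0, and the true effect is 0.

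Bias ≈ reliability × slope × shift × share of patients shifted

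| Case | Formula, minutes | Simulation, minutes |
|---|---|---|
| 30% shifted, reliability 0.8 | 0.8×2×2×0.3 = 1.0 to 0.8×3×3×0.3 = 2.2 | 0.9–2.3 |
| 30% shifted, reliability 0.6–1.0 | 0.6×2×2×0.3 = 0.7 to 1.0×3×3×0.3 = 2.7 | 0.7–2.9 |
| All shifted, reliability 0.8 | 0.8×2×2 = 3.2 to 0.8×3×3 = 7.2 | 3.1–7.3 |

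The simulation was a gamma log-link model (the SAP names no link). The first row is 0.9/16 = 6% to 2.3/16 = 14% of the target. In standard errors it is 0.9/3.45 = 0.26 to 2.3/3.45 = 0.67, which implies a 5% test rejecting about 6% to 10% of the time; the simulation gave 5.7–9.8%.

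A second calculation let antibiotic delay itself raise APS, in a linear model with the effect implied by Protocol 7.3, 0.30 × (170 − 50) = 36 minutes. At 30% activation the bias was −0.8 to +2.8 minutes for 0–3 points per hour of delay, and +4.3 to +9.3 at an extreme 6 points per hour.

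**5. Mortality (all inputs assumed).** Log-odds of death 0.05–0.08 per APS point, a 2–3 point fall, 15–16% deaths.

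- Share removed if the whole benefit runs through physiology: 57–63% at reliability 0.6, 73–79% at 0.8, about 100% at 1.0. If half does: 30–52%. The second calculation gives 56–69% if half does.
- Total benefit at 30% activation: 0.3×0.05×2 = 0.03 to 0.3×0.08×3 = 0.07 log-odds.
- Standard error at 15% deaths: √[(2/1650 + 2/2200)/(0.15×0.85)] = 0.13.
- In the second calculation the amount removed reached 0.174 − 0.054 = 0.12 and 0.304 − 0.151 = 0.15. Those cells assume total effects of roughly 0.174/0.3 = 0.58 and 0.304/0.3 = 1.0 log-odds in activated patients, which are very large.

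**6. What arrival covariates would give up.** If true severity at the intervention ED changes by 2–3 APS points, residual primary bias is 0.7–1.9 minutes with the present list. With arrival covariates it is 2.0–4.5 if they capture half of severity variance, and 1.2–6.2 over 70% to 30%.

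**The case against.** **The primary bias is modest and rests on chosen inputs.** This stands. Against the implied 36-minute effect it is 0.9/36 = 3% to 2.3/36 = 6%. A reader might infer that the primary result is invalid, or that the scores are known to be post-treatment. The documents support neither. The window is unstated, and Protocol 8.1.3 says the programme brings forward care patients would have had later anyway, so a 24-hour score may move little.

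**The 30% figure is not a plan.** Correct: Protocol 2.4.9 and 7.3 give it as a conservative power assumption. Higher activation would enlarge the bias.

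**Arrival covariates are not plainly better.** This also stands. The post period is February 2020 to February 2021, when case mix may change differently between sites. For mortality, on the assumptions above, switching to arrival covariates (reliability 0.5 against 0.8) adds about 0.03–0.07 log-odds of case-mix bias and recovers about 0.02–0.05. That argues against making them the main model.

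**A gap between the two estimates would not identify its cause.** True. The assumed protocol effect opens a gap of 0.9–2.2 minutes, case-mix change alone 0.4–4.4, and chance stays within 0.9–1.9 in 95% of runs. A numerical trigger would mislead, but this is no reason to withhold the second estimate.

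**Secondary outcomes are labelled hypothesis generating.** The label limits the weight of the mortality part. It concerns multiplicity, however, and does not change what the adjusted coefficient estimates.

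**Conclusion.** The point holds, with moderate confidence, as a gap worth closing before analysis and not as a flaw in the main design. Both scores probably include values recorded after exposure starts, the plan's own graph does not require them, and no planned primary or secondary analysis shows the result without them. The safety models drop ED SOFA but keep `aps_24h`.

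For the primary outcome the bias can take either sign. It is about 1–3 minutes under moderate assumptions at 30% activation, and larger with more activation or a steeper link between delay and physiology.

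For mortality, a material share of any benefit through early physiology would be removed, and the share depends on the model. With the main inputs the absolute amount is small against 0.13 log-odds; it approaches one standard error only with very large assumed effects. A reader might infer that a null mortality finding would be produced by the adjustment. At these sizes, imprecision alone could explain one. What does follow is that the score-adjusted estimate is not the total effect.

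The cohort is also selected on in-ED SOFA. That is a separate matter, which neither this point nor its fix resolves.

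**What to change.** 1. State the time windows of `aps_24h` and `sofa_ed`.
2. Keep the present models as main. Prespecify a sensitivity analysis for door-to-antibiotic time, the 3-hour outcome, mortality, length of stay and charges that replaces the two scores with first-recorded heart rate, respiratory rate, oxygen saturation and GCS. Keep every other listed covariate, including infection source. Report both estimates side by side without a numerical trigger, say that a gap may reflect a protocol effect or case-mix change, and do not present the score-adjusted mortality result as the total effect.
3. If the propensity-weighted fallback is used, repeat it without acute physiology score, ED SOFA and the lactate item.
4. In the graph, add arrows from exposure to APS and to SOFA, or justify their absence.

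The cost is SAP text and a little more analysis. The high-risk cohort already needs first-recorded GCS, respiratory rate and oxygen saturation ("First-recorded vital sign data meets ≥2 of"), and the propensity score already needs first heart rate. The main model and its power are unchanged. In the simulation the arrival-covariate standard error was about 1.5% larger on average. The downside is weaker control of case-mix change in the 2020–21 post period, which is why this set is not proposed as the main model.

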#### Safety outcome analysis covariates

Variables listed below are included in multivariable analyses for primary and secondary outcomes listed above. Variables are also included in any associated subgroup, heterogeneity of treatment, and sensitivity analyses.

- Age (**age**, continuous)
- Female sex (sex, binary)
- Weighted Elixhauser comorbidity score (elixhauser\_vw, continuous)
- Insurance (insurance, categorical)
- First-available temperature in ED (vs\_temp\_cat, categorical)
- First-available systolic blood pressure in ED (**vs\_sbp**, continuous)
- Acute physiology score (aps\_24h, continuous)

**Figure 3. Adjustment variables for safety outcome multivariable analyses.** The primary exposure is arrival to the intervention ED post-intervention. White symbols indicate potential confounders or precision variables included in the multivariable model, red variables indicate potential confounders not required for the minimal adjustment set, gray symbols represent an unobserved confounder, and blue symbols (other than the outcome) represent an outcome ancestor not included in the multivariable multivariable model.

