#### 6.5 Variables/data elements

- Patient medical record number(s)
- Patient encounter ID code
- Hospital/facility
- Date of birth
- Age
- Sex
- Race

- Ethnicity
- Marital status
- Preferred language
- Insurance status/type
- Address/zip code (for determination of residence at a nursing facility or other long-term care facility and estimation of socioeconomic status)
- Social Security Number (to assist matching of encounter data to Social Security Death Index and Utah state death records)
- ED disposition
- Hospital disposition
- Date/time of all events related to ED visit and hospitalization (e.g. ED arrival & departure, hospital admission & discharge)
- Date/time antibiotics administered
- Antibiotic utilization
- APACHE II score
- APACHE IV score
- Acute physiology score
- Charlson index
- Elixhauser index
- SOFA score
- Baseline SOFA score over preceding 10 years
- Source of admission (e.g. home, SNF, LTAC, outside hospital)
- Source of infection
- Clinician infection determination, patient illness severity, sepsis status, and agreement with Code Sepsis activation
- Sepsis presence/absence
- Culture results
- Admission diagnosis
- Mode of arrival to ED
- ED triage data including triage acuity score
- Resident involvement in ED care
- Results of all laboratory testing
- Date/time of all laboratory testing
- ED length of stay
- ED vital signs
- ED medications
- ED interventions/procedures
- Date/time, elapsed time, and type of ED events including provider interaction, room placement, disposition
- Date/time of diagnostic testing, vasopressor initiation and other interventions, and management
- Date/time of interventions
- Date/time of blood or body fluid cultures
- Discharge diagnosis and procedure codes
- Billing diagnosis and procedure codes
- Diagnosis-related group
- Hospital length of stay

Code Sepsis I protocol Version 3.0

- In-hospital mortality
- Long-term mortality (e.g. 30d, 90d and 1y mortality)
- Healthcare charges
- ED patient census
- Number of ED beds
- ED patient flow (including counts of patient arrivals, boarding, and admissions)
- Attending physician ED staffing
- Nurse staffing
- Trauma registration status
- Allergies
- Adverse drug reaction events and date/time
- Code Sepsis team activation (Y/N)
- Code Sepsis activation date/time
- Code Sepsis care process completion date/times
- Code Sepsis team function
- Code Sepsis team composition (by role)
- Code Sepsis process adherence

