## Missing data

Patients with missing outcome data will be excluded from the analyses for that outcome exposure. Exposure data (study hospital and study phase) is expected to be 100% non-missing. Data is also expected to be 100% non-missing for all eligible encounters for covariates for primary/secondary outcome multivariable models. However, if this is not the case for primary and secondary outcome analyses, we will apply the following approaches based on multiple imputation using chained equations (10 datasets, results combined using Rubin's rules):

- 100% of eligible encounters with complete data: perform complete case analysis.
- ≥95% of eligible encounters with complete data: perform complete case analysis for the main outcome reporting/interpretation multivariable analysis; use multiple imputed data as a sensitivity analysis.
- <95% of eligible encounters with complete data: use multiple imputed data for the main outcome reporting/interpretation multivariable analysis; perform complete case analysis as a sensitivity analysis.

For safety outcomes, there is expected to be missingness for some prespecified covariates for patients included in "all ED" and "sepsis mimic" cohorts.

- 100% of eligible encounters with complete data: perform complete case analysis.
- ≥95% of eligible encounters with complete data: perform complete case analysis for the main outcome reporting/interpretation multivariable analysis; use multiple imputed data as a sensitivity analysis.
- <95% of eligible encounters with complete data: use multiply imputed data for the main outcome reporting/interpretation multivariable analysis; perform complete case analysis as a sensitivity analysis.

Where performed, multiple imputation models will be performed separately for primary/secondary vs safety outcomes. Variables included in the model will include each outcome (within the outcome class), study site, study phase, all covariates (within the outcome class), and additional potentially-informative variables identified based on expert opinion and literature review. We will use predictive mean matching using five nearest neighbors for imputation of continuous variables and logistic regression with bootstrap for binary variables.

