#### Primary and secondary analyses

```
dag {
"Arrival to intervention ED post-intervention" [exposure,pos="-1.196,0.491"]
"Door-to-antibiotic time" [outcome,pos="1.007,0.477"]
"ED arrival mode" [adjusted,pos="-0.485,0.630"]
"Elixhauser score" [adjusted,pos="0.565,-0.356"]
"Illness severity" [latent,pos="-0.139,0.781"]
"Initial SBP" [adjusted, pos="-0.104, 1.525"]
"Long-term care" [adjusted,pos="-1.122,-0.086"]
"O2 sat" [pos="1.453,0.736"]
"Preferred language" [adjusted,pos="-0.378,-0.501"]
"SOFA score" [adjusted,pos="0.269,1.938"]
"Suspected infection source" [adjusted,pos="0.536,-1.411"]
APS [adjusted, pos="-0.561, 1.300"]
Age [adjusted, pos="-1.631, -0.018"]
GCS [pos="0.214,0.680"]
HR [pos="1.331,1.495"]
Lactate [pos="0.977,2.039"]
RR [pos="1.106,1.680"]
Sex [adjusted,pos="-1.399,-0.383"]
Temperature [pos="0.798,1.651"]
WBC [pos="1.406,1.039"]
"Arrival to intervention ED post-intervention" -> "Door-to-antibiotic time"
"ED arrival mode" -> "Arrival to intervention ED post-intervention"
"ED arrival mode" -> "Door-to-antibiotic time"
"Elixhauser score" -> "Arrival to intervention ED post-intervention"
"Elixhauser score" -> "Door-to-antibiotic time"
"Elixhauser score" -> "Illness severity"
"Elixhauser score" -> "Long-term care"
"Illness severity" -> "ED arrival mode"
"Illness severity" -> "Initial SBP"
"Illness severity" -> "SOFA score"
"Illness severity" -> APS
"Illness severity" -> GCS
"Initial SBP" -> "Door-to-antibiotic time"
"Initial SBP" -> "SOFA score"
```

```
"Initial SBP" -> APS
"Initial SBP" -> Lactate
"Long-term care" -> "Arrival to intervention ED post-intervention"
"Long-term care" -> "ED arrival mode"
"Long-term care" -> "Suspected infection source"
"O2 sat" -> "Door-to-antibiotic time"
"O2 sat" -> "SOFA score"
"O2 sat" -> APS
"Preferred language" -> "Arrival to intervention ED post-intervention"
"Preferred language" -> "Door-to-antibiotic time"
"Preferred language" -> "ED arrival mode"
"SOFA score" -> "Door-to-antibiotic time"
"Suspected infection source" -> "Door-to-antibiotic time"
"Suspected infection source" -> "Illness severity"
APS -> "Door-to-antibiotic time"
Age -> "Arrival to intervention ED post-intervention"
Age -> "Door-to-antibiotic time"
Age -> "ED arrival mode"
Age -> "Long-term care"
Age -> "Preferred language"
GCS -> "Door-to-antibiotic time"
GCS -> "SOFA score"
GCS -> APS
HR -> "Door-to-antibiotic time"
HR \rightarrow APS
Lactate -> "Door-to-antibiotic time"
RR -> "Door-to-antibiotic time"
RR -> APS

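### The safety models omit ambulance arrival, so a case-mix change that differs between the intervention and control EDs could bias the all-ED antibiotic-use comparison

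*SAP*

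**What the plan says.** The SAP section on safety outcome analysis covariates lists seven adjusters: age, sex, weighted Elixhauser score, insurance, "First-available temperature in ED", first systolic blood pressure (SBP), and APS, entered as "Acute physiology score (aps\_24h, continuous". The 24-hour window is inferred from that variable name. The section's opening sentence refers to primary and secondary outcomes; I take this as a slip for safety outcomes. The next sentence extends the list: "Variables are also included in any associated subgroup, heterogeneity of treatment, and sensitivity analyses".

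The corresponding list for primary and secondary outcomes includes "Arrival to ED via ambulance". In the SAP Appendix, the diagram code for those analyses draws ED arrival mode as a cause of both the exposure and door-to-antibiotic time, and latent illness severity as a cause of arrival mode. The code for the safety analyses has the same exposure node but no arrival-mode node. No reason is given.

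Protocol 6.5 lists both "Mode of arrival to ED" and "ED triage data including triage acuity score" among the data elements.

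The SAP's Data analysis section says that every multivariable model adjusts for factors plausibly related to the outcome and to treatment hospital, phase or Code Sepsis activation. It plans propensity weighting if a parallel-trends test on pre-implementation data fails. The weights gain ambulance arrival only for cohorts of patients with sepsis, and they never include triage acuity.

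Under Missing data, the SAP states that "there is expected to be missingness for some prespecified covariates for patients included in" the all-ED and sepsis-mimic cohorts. It names no variable and gives no rate. Below 95% completeness, multiple imputation is the main analysis.

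**The concern.** All-ED antibiotic use is the broadest check on whether faster sepsis care leads to wider prescribing. Protocol 3.2 hypothesises faster antibiotics without more overtreatment, and Protocol 3.5 makes continuation or spread of the programme contingent on the results.

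Antibiotic use per visit depends on who comes through the door. If the mix of sicker and less sick patients moves differently at the intervention ED than at the controls during phase 3 (February 2020 to February 2021), the DID changes with no change in prescribing. The bias could create a false harm signal or hide a real one. Arrival mode is a marker of case mix that is fixed before ED care begins, and the plan already treats it as a confounder elsewhere.

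**Working it through.** **1. Consistency of the two diagrams.** What causes a patient to arrive at the intervention ED in phase 3 cannot depend on which outcome is analysed later. The arrow from arrival mode to the exposure should therefore appear in both diagrams or in neither. Suppose the primary diagram's arrows (illness severity to arrival mode, arrival mode to exposure) are placed in the safety diagram, with no direct arrow from arrival mode to the safety outcome. A path still runs from exposure through arrival mode, severity, APS and heart rate to the outcome. Adjusting for APS, a common effect of severity and heart rate, opens that path. Adjusting for arrival mode closes it.

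**2. Do the safeguards cover it?** The parallel-trends test uses pre-phase data, so a shift beginning in phase 3 cannot trigger the weighting. If the weighting were triggered, the all-ED weights would still lack ambulance arrival. The interrupted time series covers the primary outcome only. Imputation fills in listed covariates but does not adjust for unlisted ones.

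**3. Size.** The plan states no precision or power figure for any safety outcome, so there is nothing to reproduce. What follows is an illustration.

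*From the documents* (Protocol 4.1, Table 1): annual visits of 89,000 at the intervention ED and 49,000 + 65,000 = 114,000 at the controls, used for each phase.

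*Assumed*: antibiotic use of 20% at high and 5% at low acuity; high-acuity share of 20% at both in phase 1; 25% at the controls and 25% + d at the intervention ED in phase 3; two-sided 5% test; clustering ignored.

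Formulas, with a = fraction of the shift absorbed by the listed covariates:

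- Bias = d × (0.20 − 0.05) × (1 − a)
- SE = √Σ p(1 − p)/n over the four cells

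Cell rates:

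- Phase 1, both: 0.20 × 0.20 + 0.80 × 0.05 = 0.080
- Phase 3, controls: 0.25 × 0.20 + 0.75 × 0.05 = 0.0875
- Phase 3, intervention, at d = 0.023: 0.0875 + 0.15 × 0.023 ≈ 0.091

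SE = √(0.0736/114,000 + 0.0736/89,000 + 0.0798/114,000 + 0.0827/89,000) ≈ 0.00176, or 0.176 percentage points (pp).

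Bias needed for z = 1.96: 1.96 × 0.176 = 0.345 pp.

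- Severity unadjusted (a = 0): 0.345/0.15 = **2.3 points** of extra high-acuity share
- Half absorbed (a = 0.5): 0.345/0.075 = **4.6 points**

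Varying high-acuity use from 15% to 30%:

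| Extra shift | Absorbed | Bias (pp) | Chance of p < 0.05 |
|---|---|---|---|
| 0 | any | 0 | 5% |
| 2 points | none | 0.20–0.50 | 23–72% |
| 2 points | half | 0.10–0.25 | 9–25% |
| 5 points | none | 0.50–1.25 | 86–100% |
| 5 points | half | 0.25–0.63 | 33–88% |
| 5 points | 80% | 0.10–0.25 | 9–24% |

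**4. Fewer patients.** Table 1 counts visits, whereas the cohort takes adult, non-trauma first visits. With an assumed 60,000 and 77,000 per phase and 8–10% use, SE = √[p(1 − p)(2/60,000 + 2/77,000)] = 0.21–0.23 pp. The thresholds rise to 1.96 × 0.21/0.15 = 2.7 and 1.96 × 0.23/0.15 = 3.0 points, or about 5.5 to 6 if half is absorbed.

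**5. A common shift.** If d = 0, the linear DID is (0.0875 − 0.080) − (0.0875 − 0.080) = 0. On the logit scale, a common 5-point shift from unequal starting shares (15% and 25%) gives a ratio of odds ratios of 0.97–0.99, so little is left.

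**The case against.** Several points on the other side stand.

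- **Common shifts cancel.** A reader might infer that a pandemic change in ED case mix will be read as a change in prescribing. The documents do not support that. The DID subtracts the concurrent change at the control EDs, all three EDs belong to one health system, and neither document describes a differential shift.
- **Severity is already partly adjusted for.** First temperature, first SBP and APS are all in the model.
- **APS completeness is unknown.** A reader might infer that most low-acuity patients lack APS. The SAP does not name APS as the incomplete variable. Its safety diagram shows APS fed by five bedside measures and one laboratory value (white cell count). Multiple imputation, with further auxiliary variables allowed, is planned.
- **Triage acuity is not clearly a baseline value.** A reader might want it as the main severity adjuster in place of APS. Protocol 5.2 lets Code Sepsis identification happen at triage, puts the triage nurse on the team and continues training through phase 3. Scoring at the intervention ED could therefore change because of the intervention, and adjusting for it could remove part of the effect.
- **A less exposed analysis exists.** Antibiotic use is also analysed in the sepsis high-risk cohort, defined by first recorded vital signs. A fall in low-acuity visits would barely change that denominator.
- **Safety results are labelled hypothesis generating.** That label concerns multiplicity; it does not address confounding.

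It can also be said that an arrow to door-to-antibiotic time does not carry over to safety outcomes. That is so for the outcome arrow, but not for the arrow into the shared exposure. None of these points explains why ambulance arrival was dropped.

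**Conclusion.** The omission is real and conflicts with the SAP's own adjustment rule and its own primary diagram. It leaves all-ED antibiotic use open to bias from a phase 3 case-mix change that differs between sites, and the planned fallback would not repair this. Sepsis-cohort safety outcomes share the inconsistency, since the same patients' primary and secondary models do adjust for ambulance arrival.

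The size is conditional. Under the stated assumptions, about 2.3 extra points of high-acuity share reach nominal significance with severity unadjusted, and about 4.6 if the listed covariates absorb half. With fewer eligible visits the figures are about 2.7–3.0 and 5.5–6. The antibiotic-use rates, acuity shares, size of shift and absorbed fraction are all assumed. Nothing was computed for adverse reactions, C. difficile or the mimic cohort. The point does not affect the primary outcome, and it does not show that bias will occur.

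**What to change.** - Add ambulance arrival to the safety covariate list, to the safety diagram with its arrow to the exposure, and to the safety imputation model. Keep APS in the main model.
- Add triage acuity in a sensitivity model only, stating that Code Sepsis may influence triage scoring at the intervention ED.
- Report acuity mix and APS completeness by site and phase, so that readers can judge whether a differential shift occurred.

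The cost is a few lines of SAP text, one extra model and one descriptive table. Both variables are already collected, and one binary covariate costs nothing of note at this sample size. Ambulance arrival removes the bias only as far as it tracks the shift in case mix, which is why the descriptive table is needed as well.
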